Patients who successfully complete the open-label run-in and continue to meet all inclusion/exclusion criteria will be randomized (1:1 ratio) on the last day of the run-in period (Day 0) to either Sequence 1 or 2. Subjects randomized to Sequence 1 will receive Treatment A (amifampridine phosphate or placebo) in Period 1 and Treatment B (the other treatment) in Period 2. Subjects randomized to Sequence 2 will receive Treatment B (amifampridine or placebo) in Period 1 and Treatment A (the other treatment) in Period 2. Study medication (amifampridine phosphate tablets or placebo tablets) for Period 1 will be dispensed on Day 0, the last day of the Run-in, by the site pharmacist, according to the randomization schedule.

The administration of blinded medication will begin only after completion of all assessments of Day 0. The Day 0 assessments are performed while taking a dose of open-label amifampridine phosphate in the clinic, 40 minutes before starting the assessments. Any supply of open-label amifampridine phosphate should be collected by the study site and stored before dispensing the Period 1 blinded medication.

The patient will receive either blinded amifampridine phosphate tablets or placebo tablets for 8 days as an outpatient, and a dose of the same medication on the day of scheduled study visit (Day 8) in the clinic, in order to facilitate efficacy assessments, under double-blind conditions. If the patient is on a BID or TID regimen during Period 1, the Day 8 assessments should occur after the same dose that corresponds to when assessments were done on Day 0. All unused medication and the container must be brought back to the study site at the end of Period 1. **The Day 8 medication is the same as double-blind medication taken for the previous Period 1 days.** Any unused portion of dispensed drug will be returned to the pharmacy before dispensing drug for the Re-Stabilization Period. A dose of medication for Day 8 must be administered by research study staff, in the clinic, in order to perform evaluations within specified time periods, as described in Section 10.3.3.

Re-stabilization Period (Days 9-21) (+1 day)

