The site pharmacy will dispense bottles containing blinded amifampridine phosphate or placebo tablets, depending on the patient's Treatment Sequence assignment, for daily outpatient administration for 7 days (Days 1-7). Administration of blinded study medication will begin with the next scheduled dose following the Day 0 baseline assessment on open-label medication. (see Section 13.3).

13.3 Period 1

Administration will be continued on an outpatient basis for a total of 7 days (Days 1-7).

On Day 8 (+1) patients will be given a dose of the same study medication as the previous 7 days by the study personnel, at the site, so that the assessments/procedures listed below will be completed in relation to the time of study medication dosing.

- Assessment of AEs/SAEs;
- Abbreviated physical exam with weight;
- Vital signs (seated position), including SBP, DBP, heart rate, respiration, and body temperature;
- Clinical laboratory tests;
- Concomitant medications;
- IP accountability;
- Efficacy assessments, including:
 - MFM 20 or 32;
 - SGI (patient/parent/guardian/caregiver);
 - Stimulated Single fiber EMG (optional);
 - CGI-S;
 - CGI-I; and

- Slurp test (optional).

Assessment	Start Time After Dose* (± 10 minutes unless otherwise specified)
SGI	40 minutes
MFM 20 or 32	after SGI
Stimulated Single fiber EMG	after MFM
Slurp test, CGI-S and CGI-I	At end of assessments

*Administration of medication represents Time 0 (minutes)

If the stimulated single fiber EMG (optional assessment) is not to be performed, then the slurp test (also optional), CGI-S and CGI-I assessments should be done following completion of the MFM.

Open-label amifampridine phosphate will be dispensed at the Day 8 visit for administration during the stabilization period, starting with the next scheduled dose after Day 8 assessments (see Section 13.4).

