13.4 Re-stabilization Period

Patients will return to their prior open-label amifampridine phosphate dose established in the run-in phase for 2 weeks, Day 9 through Day 21.

Patients will report to the study site on Day 21 (+1 day) and have the assessments/procedures listed below completed.

- Assessment of AEs/SAEs;
- Abbreviated physical exam with weight;
- Vital signs (seated position), including SBP, DBP, heart rate, respiration, and body temperature;
- Urine pregnancy test in females of childbearing potential only;
- Concomitant medications;
- IP accountability;
- Efficacy assessments, including:
 - MFM 20 or 32;

- SGI (patient/parent/guardian/caregiver);
- CGI-S;
- CGI-I; and
- Slurp test (optional).

Assessment	Start Time After Dose* (\pm 10 minutes unless otherwise specified)
SGI	40 minutes
MFM 20 or 32	after SGI
Slurp test, CGI-S and CGI-I	At end of assessments

*Administration of medication represents Time 0 (minutes)

A The slurp test (optional), CGI-S and CGI-I assessments should be done following completion of the MFM.

The site will dispense bottles containing amifampridine phosphate or placebo tablets, depending on the patient's Treatment Sequence assignment, for Period 2 (Days 22-28). Administration of blinded study medication will begin with the next scheduled dose after Day 21 assessments are completed (see Section 13.5).

13.5 Period 2

Patients will the blinded study medication they did not receive in Period 1. Administration will be continued on an outpatient basis for a total of 7 days (Days 22-28).

Patients will report to the study site on Day 29 (+1 day) and receive a dose of the same study medication they received for the previous 7 days, under the supervision of the study personnel, in order to time the following assessments/procedures in relation to the medication dose.

- Assessment of AEs/SAEs;
- Complete physical exam with weight;
- Vital signs (seated position), including SBP, DBP, heart rate, respiration, and body temperature;
- Standard resting 12-lead ECG;
- Clinical laboratory tests;

- Urine pregnancy test in females of childbearing potential only;
- Concomitant medications;
- IP accountability;
- Efficacy assessments, including:
 - MFM 20 or 32;
 - SGI (patient/parent/guardian/caregiver);
 - Stimulated single fiber EMG (optional);
 - CGI-S;
 - CGI-I; and
 - Slurp test (optional).

Assessment	Start Time After Dose* (± 10 minutes unless otherwise specified)
SGI	40 minutes
MFM 20 or 32	after SGI

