15.4 Laboratory Tests

For each laboratory parameter, descriptive statistics will be presented for the observed value and CFB by treatment at the time of the assessment. The frequency and percentage of patients who experience abnormal (i.e. outside of reference ranges) laboratory values will be presented by treatment at the time of the assessment. Clinically significant abnormalities will be collected as AEs.

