5.0 Analysis of Safety

The following describes the statistical analysis of safety data.

Adverse Events

Prior to analysis, all AEs will be coded using the Medical Dictionary for Regulatory Activities (MedDRA). A treatment-emergent adverse event (TEAE) is any AE that occurs after the start of treatment. All TEAEs will be summarized by the treatment at the time of onset. Counts and percentages will be presented by treatment for each observed system organ class (SOC) and preferred term (PT) as defined in MedDRA. Summaries by level of severity and relationship to treatment will be presented by treatment at the time of occurrence. Listings of all deaths, serious AEs (SAEs), and discontinuations due to AE will be provided.

An overall summary table will provide the highest relationship and maximum severity observed per subject, as well as the counts of patients who: discontinued early due to an AE, experienced death, or had at least one SAE.

Laboratory Tests

For each laboratory parameter, descriptive statistics will be presented for the observed value and change from baseline (CFB) by treatment, where CFB is the change from the previous assessment. The frequency and percentage of patients who experience

abnormal (i.e. outside of reference ranges) laboratory values will be presented by treatment and time point.

Concomitant Medications

A table of the WHO-coded medications will be constructed by treatment given in the study period (amifampridine or placebo) and overall with medications summarized by level 4 Anatomical Therapeutic Chemical (ATC) term and Preferred Term. The number and percent of patients on each drug will be summarized. A data listing for all concomitant medications will be provided.

Vital Signs

Summary statistics (mean, median, sample size, standard deviation, minimum, and maximum) will be computed on the raw and change from baseline values for each vital sign parameter by time point, for each treatment. The screening time point will serve as baseline. If there are multiple vital signs taken at any time point, then the latest set of vital signs will be used for the analysis. All vital sign data will be listed.

ECG Results

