Preferred Term 2	xxx (xxx%)	xxx (xxx%)	xxx (xxx%)

^a The denominator for all percentages will be the number of patients in the safety population.

^b Medications coded with WHO Coding Dictionary xxxxxxxx.

STATKING Clinical Services (yyyy-mm-dd)

Source Program: xxxxxxx.sas

Table 46. Clinical Laboratory Summary Statistics by Treatment and Time Point
 Catalyst Pharmaceuticals, Inc. - CMS-001
 Safety Population (N=xxxx)

Laboratory Parameter (units)	Treatment Sequence	Time Point	Data Type ^a	Mean	Std Dev	n	Min	Max	Median
xxxxxxxxxxxxxx (xxxx)	Amifampridine/Placebo	Screening	RAW	xxx	xxx	xxx	xxx	xxx	xxx
			RAW	xxx	xxx	xxx	xxx	xxx	xxx
		Day X	CFP	xxx	xxx	xxx	xxx	xxx	xxx
	Placebo/Amifampridine	Day X	RAW	xxx	xxx	xxx	xxx	xxx	xxx
			CFP	xxx	xxx	xxx	xxx	xxx	xxx
		Day X	RAW	xxx	xxx	xxx	xxx	xxx	xxx
			CFP	xxx	xxx	xxx	xxx	xxx	xxx

^a RAW = observed data recorded in database; CFP = change from previous assessment = Value at Timepoint - Value at Previous Assessment.
 STATKING Clinical Services (yyyy-mm-dd)
 Source Program: xxxxxxx.sas

Table 47. Number and Percent of Patients with Abnormal Laboratory Results by Treatment and Time Point
Catalyst Pharmaceuticals, Inc. - CMS-001
Safety Population (N=xxxx)

Laboratory Parameter (units)	Time Point	Treatment at Time of Assessment	
		Amifampridine	Placebo
xxxxxxxxxxxx	Screening	xxx (xxxx%)	xxx (xxxx%)
	Day X	xxx (xxxx%)	xxx (xxxx%)
	Screening	xxx (xxxx%)	xxx (xxxx%)
	Day X	xxx (xxxx%)	xxx (xxxx%)

STATKING Clinical Services (yyyy-mm-dd)
Source Program: xxxxxxx.sas

Table 48. Vital Sign Parameters Summary Statistics
Catalyst Pharmaceuticals, Inc. - CMS-001
Safety Population (N=xxxx)

Treatment Sequence	Vital Sign Parameter (units)	Visit	Data Type ^a	Mean	Std Dev	n	Min	Max	Median
Amifampridine/Placebo	xxxxxxxxxx (xxx)	Screening (Baseline)	RAW	xxx	xxx	xxx	xxx	xxx	xxx
		Day X	RAW	xxx	xxx	xxx	xxx	xxx	xxx
			CFP	xxx	xxx	xxx	xxx	xxx	xxx
Placebo/Amifampridine	xxxxxxxxxx (xxx)	Screening (Baseline)	RAW	xxx	xxx	xxx	xxx	xxx	xxx
		Day X	RAW	xxx	xxx	xxx	xxx	xxx	xxx
			CFP	xxx	xxx	xxx	xxx	xxx	xxx

^a RAW = observed data recorded in database; CFP = change from previous assessment = Value at Timepoint - Value at Previous Assessment.
STATKING Clinical Services (yyyy-mm-dd)
Source Program: xxxxxxx.sas

Page x of y

Table 49. Electrocardiogram Parameters Summary Statistics
 By Treatment and Time Point
 Catalyst Pharmaceuticals, Inc. CMS-001
 Safety Population (N=xxxx)

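### The Day 29 laboratory change is taken from Day 8, when the patient was on the opposite treatment, so the Period 2 treatment contrast in laboratory change is doubled

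*SAP*

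**What the plan says.** Protocol 15.4 (Laboratory Tests) says that "descriptive statistics will be presented for the observed value and CFB by treatment at the time of the assessment". It names no baseline visit. SAP 5.0 (Laboratory Tests) supplies a definition: change is presented by treatment, "where CFB is the change from the previous assessment". The Table 46 shell in SAP Appendix B follows that definition, with the footnote "CFP = change from previous assessment = Value at Timepoint - Value at Previous Assessment". Its title refers to treatment and time point, but its grouping column is treatment sequence.

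For vital signs, SAP 5.0 states: "The screening time point will serve as baseline". The Table 48 shell marks Screening as baseline, yet its footnote defines change in the same words as Table 46.

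Elsewhere the SAP uses fixed references. The efficacy analyses in 4.2.1 and 4.2.2 use Day 0 for Period 1 and Day 21 for Period 2, and the ECG analysis uses Screening. No reason is given for treating laboratory data differently.

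**The concern.** In a crossover, a rule that takes change from the preceding sample is harmless only if that sample is taken in a comparable state in both sequences. For laboratory data it is not. No sample is scheduled at the end of re-stabilization, so the sample before Day 29 is the one at the end of Period 1, on the opposite blinded treatment. One label then covers two different quantities: blinded treatment against open-label drug at Day 8, and one blinded treatment against the other at Day 29.

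Safety and tolerability compared with placebo is a primary objective (Protocol 9.1). Liver enzymes are among the scheduled tests (Protocol Table 6), and Protocol 8.4.4 lists abnormal liver enzymes among earlier clinically significant or serious events. A reader comparing the Day 29 change rows of the two sequences would see a difference twice as large as the observed values support.

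**Working it through.** The documents state no figure on this point, so there is none to reproduce. The check sets out the visit schedule and follows the expected means.

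**Inputs**

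- Laboratory visits: Screening (Protocol 13.1), Day 0 (13.2, where "Clinical laboratory tests" is listed), Day 8 (13.3) and Day 29 (13.5). The Day 21 list in 13.4 contains no laboratory tests, and Table 3 agrees.
- State at Day 0: "The Day 0 assessments are performed while taking a dose of open-label amifampridine phosphate in the clinic, 40 minutes before starting the assessments" (10.1). Randomization also requires at least 7 days on a stable dose. Protocol 10.3.3 places the laboratory draw before the clinic dose, so *on drug* here means during that dosing regimen.
- State before Period 2: "Patients will return to their prior open-label amifampridine phosphate dose established in the run-in phase for 2 weeks, Day 9 through Day 21" (13.4).
- Period 2 treatment: "Patients will the blinded study medication they did not receive in Period 1" (13.5). Day 8 and Day 29 are therefore always on opposite treatments.
- Allocation to sequences is 1:1 (10.3.4).
- Assumed, because the documents give no values: an additive drug effect d, a fraction r of it lost by the end of a placebo period (range 0.5 to 1), no period effect, and no extra samples.

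**Expected values above the off-drug level**

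| Sequence | Day 0 | Day 8 | Day 29 |
|---|---|---|---|
| Amifampridine, then placebo | d | d | (1−r)d |
| Placebo, then amifampridine | d | (1−r)d | d |

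**Laboratory change as the SAP defines it**

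| Sequence | Day 8 minus Day 0 | Day 29 minus Day 8 |
|---|---|---|
| Amifampridine, then placebo | 0 | −rd |
| Placebo, then amifampridine | −rd | +rd |

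**Contrasts, amifampridine minus placebo**

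- Day 8: 0 − (−rd) = rd.
- Day 29: rd − (−rd) = 2rd. This is the between-sequence comparison in Table 46.
- Pooled by treatment: amifampridine (0 + rd)/2 = 0.5rd; placebo (−rd − rd)/2 = −rd; difference 1.5rd.
- Unequal sequences: with fraction f in the amifampridine-first sequence, the pooled contrast is (1−f)rd + rd = (2−f)rd. For 23 patients split 11 and 12 this is 1.48rd to 1.52rd.

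**Range over r**

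| r | Day 8 | Day 29 | Pooled |
|---|---|---|---|
| 1 | 1.00d | 2.00d | 1.50d |
| 0.67 | 0.67d | 1.34d | 1.005d |
| 0.5 | 0.50d | 1.00d | 0.75d |

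A simulation with r = 1 and 200,000 patients per sequence gave a pooled contrast of 1.503d under the SAP definition and 1.000d with a Day 0 baseline.

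**With Day 0 as the common baseline**, the changes are 0 and −rd in the first sequence, and −rd and 0 in the second. The contrast is rd at Day 8, at Day 29 and pooled. This equals the contrast in the observed values: d − (1−r)d = rd.

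**Vital signs.** These are measured at Day 21 (13.4), on open-label drug in both sequences. Under the Table 48 footnote, the Day 29 change is measured from an expected d in both sequences. It is −rd on placebo and 0 on amifampridine, a contrast of rd, the same as at Day 8. With Screening as baseline the reference has the same expectation in both sequences, so the contrast is again rd. The two definitions give different changes within a column but the same expected treatment contrast.

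**The case against.** Several points on the other side stand. The safety analysis is descriptive (Protocol 15.2), with no test or decision rule attached to laboratory change. Observed values appear beside the change rows in Table 46. Table 47 counts abnormal results by treatment at the time of assessment, Data Listing 4 gives treatment at sample collection, and clinically significant abnormalities are recorded as adverse events. None of these depends on the definition of change. The SAP states its definition openly, and Table 46 labels the row as change from the previous assessment, so nothing is concealed. The 1.5 factor arises only if the text's summary by treatment is followed literally; Table 46 is laid out by sequence and time point and has no pooled column.

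A reader might also infer stronger claims that the documents do not support.

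- That Table 48 inflates effects on heart rate or blood pressure. It does not, because Day 21 vital signs give both sequences an on-drug reference.
- That a laboratory effect could be hidden. The contrast is rd in Period 1 and 2rd in Period 2; neither falls below the observed on/off difference.
- That the table always exceeds the full drug effect d. At Day 29, 2rd > d only if r > 1/2; pooled, 1.5rd > d only if r > 2/3. What holds at every r is the inflation relative to the observable contrast rd.

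The objection limits the consequence. It does not remove the fault: the Day 29 change rows compare the two treatments with reference values taken on opposite treatments.

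**Conclusion.** The point holds for laboratory change in Period 2. The between-treatment contrast is 2 times the observable on/off difference at Day 29, and 1.5 times if pooled by treatment; Period 1 is correct. With full reversal these are 2d and 1.5d against a true d. The factors assume an additive effect and no period effect, and the pooled factor also assumes equal sequences. They further assume that Day 8 is the last laboratory sample before Day 29. Protocol 10.6.3 and 11.3 allow repeat and additional sampling, which could change which sample counts as previous for an individual patient; the SAP does not address this.

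The consequence is a misleading descriptive row in support of a primary safety objective. It does not invalidate the safety conclusions. The vital-sign issue is a separate contradiction between the SAP 5.0 text and the Table 48 shell, and must be reconciled, but it produces no inflation.

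**What to change.** In SAP 5.0, define laboratory baseline as the Day 0 value for both Day 8 and Day 29. In Table 46, change the computation and the footnote to match. Relabelling the row alone would put a wrong name on an unchanged number. State whether laboratory change is summarised by treatment or by sequence, and make the text and the shell agree. A fixed baseline also removes the dependence on unscheduled samples.

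The one drawback is that Day 0 follows the run-in on drug, so a shift that arises during run-in in a previously untreated patient would not appear in change from Day 0. Keeping change from Screening as a supplementary row covers this. Screening mixes untreated and already treated patients, so it should not be the main reference.

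For vital signs, choose one baseline and use it in both the SAP text and Table 48. Either Screening, or Day 0 and Day 21 as for efficacy, is acceptable. The latter gives the same Day 8 and Day 29 changes as the current shell, provided no measurements are added between visits.

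The cost is a few sentences in SAP 5.0 and edits to two shells. All the samples needed are already scheduled.

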15.5 Other Safety Assessments

Summary statistics for vital signs, physical examinations, and ECG parameters will be presented by treatment at the time of the assessment.

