ECG parameters will be summarized with descriptive statistics by time point and treatment sequence. A shift table of investigator classification of the ECG will be created showing Normal/Normal, Normal/Abnormal, Abnormal/Normal, and Abnormal/Abnormal frequencies by time point using the screening value as the baseline. All ECG data will be listed.

Physical Examination Findings

All Physical Examination data will be listed as shown in Appendix B.

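### The laboratory, vital-sign and ECG table shells are laid out by treatment sequence, so no planned table gives continuous laboratory or vital-sign values pooled by treatment, as the protocol leads one to expect

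*SAP*

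**What the plan says.** **Protocol.** For laboratory tests (15.4), "descriptive statistics will be presented for the observed value and CFB by treatment at the time of the assessment". For the other assessments (15.5), "Summary statistics for vital signs, physical examinations, and ECG parameters will be presented by treatment at the time of the assessment". Section 15.6 adds that any inconsistency between SAP and protocol will be noted in the SAP.

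**SAP 5.0 text.** Laboratory values are summarized "by treatment, where CFB is the change from the previous assessment". Vital signs are summarized "for each vital sign parameter by time point, for each treatment", with Screening as baseline. For ECG the rule changes: "ECG parameters will be summarized with descriptive statistics by time point and treatment sequence".

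**SAP Appendix B shells.** Table 46 is titled "Clinical Laboratory Summary Statistics by Treatment and Time Point", but its grouping column is treatment sequence, with rows Amifampridine/Placebo and Placebo/Amifampridine. Tables 48 and 49 have the same column, and Table 49 also carries a by-treatment subtitle. Table 50 (ECG shifts) uses the same two sequence rows. Table 47 (abnormal laboratory results) is headed by treatment at assessment, and Tables 41 to 44 give adverse events by treatment.

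**Status of the shells.** Under the table disclaimer in SAP Appendix A, the mock tables set the format of the delivered tables. SAP 1.0 describes the plan as consistent with Protocol Amendment 5. No departure on safety summaries is recorded.

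**The concern.** Safety and tolerability compared with placebo is the first-listed primary objective. In a two-period crossover the natural safety summary puts everything observed on amifampridine beside everything observed on placebo. A sequence layout splits each treatment between two rows and two visits. The label can also mislead: at Day 29 the row whose name begins with amifampridine holds placebo values.

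The programmer is left with two instructions. The SAP text says treatment for laboratory values and vital signs, the shells say sequence, and the shells define the deliverable. If the shells win, a protocol commitment on a primary objective is dropped without notice.

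**Working it through.** The plan states no figure on this point, so the check is a comparison of text with shells, followed by a mapping of cells to treatments.

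**1. Text against shell**

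| Data | Protocol | SAP 5.0 text | SAP shell |
|---|---|---|---|
| Laboratory values | treatment at assessment | treatment | Table 46: sequence |
| Abnormal laboratory counts | treatment at assessment | treatment | Table 47: treatment |
| Vital signs | treatment at assessment | treatment | Table 48: sequence |
| ECG parameters | treatment at assessment | sequence | Table 49: sequence |
| ECG shifts | not specified separately | time point | Table 50: sequence |

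Four of these five tables are by sequence. Only Table 47 is by treatment.

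**2. What each cell holds.** From the schedule of events (protocol Table 3 and Section 13), laboratory samples are taken at Screening, Day 0, Day 8 and Day 29. Vital signs are taken at those visits and on Day 21. ECGs are scheduled at Screening and Day 29, plus early discontinuation. For illustration, assume 23 patients split 12/11 with no dropout.

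| Sequence | Day 8 | Day 29 |
|---|---|---|
| Amifampridine/Placebo (12) | amifampridine | placebo |
| Placebo/Amifampridine (11) | placebo | amifampridine |

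Each scheduled blinded cell holds one treatment. Pooled by treatment, amifampridine has 12 + 11 = 23 observations and placebo has 11 + 12 = 23. No shell shows that pooling for continuous laboratory or vital-sign values.

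**3. The change column in Table 46.** It is the value minus the previous assessment. With no Day 21 sample, the assessment before Day 29 is Day 8:

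- Amifampridine/Placebo: Day 29 − Day 8 = placebo − amifampridine.
- Placebo/Amifampridine: Day 29 − Day 8 = amifampridine − placebo.

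The two rows estimate the same contrast with opposite signs, and nothing in the shell says so. Pooling this column by treatment would not repair it. The amifampridine column would mix Day 8 − Day 0 (blinded minus open-label amifampridine) with Day 29 − Day 8 (amifampridine minus placebo).

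Table 48 has a related fault. Its footnote defines change from the previous assessment, whereas SAP 5.0 takes Screening as the vital-sign baseline.

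**4. ECG.** With Day 29 the only scheduled ECG after randomization, completers give 12 on placebo and 11 on amifampridine, and a by-treatment layout relabels the same two cells. Early withdrawals differ. The Table 50 footnote lets end of study be the withdrawal day, so an Amifampridine/Placebo patient who leaves in Period 1 has an amifampridine ECG in a row that otherwise holds placebo ECGs. Table 49 also has a Day 0 row, although no Day 0 ECG is scheduled.

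**5. Illustration of precision, laboratory values and vital signs only.** Let σ be the standard deviation of one measurement and ρ the within-patient correlation. The documents give no ρ, so 0.4, 0.6 and 0.8 are assumptions.

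- Standard error of a treatment mean in a single cell relative to the pooled mean, taking the average cell size 23/2 = 11.5: √(23/11.5) = 1.41.
- Difference between sequences at one visit: σ√(1/12 + 1/11) = 0.417σ.
- Within-patient difference: σ√(2(1 − ρ)/23) = 0.228σ, 0.187σ and 0.132σ.
- Ratios: 1.8, 2.2 and 3.2.

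**The case against.** The strongest reply is that little is hidden. Adverse events and abnormal-laboratory counts are by treatment, sequence plus visit identifies treatment in every scheduled blinded cell, and Table 46 already contains a within-patient contrast at Day 29. Protocol 15.2 makes safety descriptive, so no test or interval loses precision and the ratios above do not describe a planned inference. SAP 2.1 states openly that summary statistics are by sequence and period. Finally, neither 15.4 nor 15.5 explicitly asks for pooling across periods or for a within-patient difference.

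Most of this stands, and it limits the point. A reader might infer that the amifampridine-placebo safety comparison is never shown, or that sequence rows blend the two treatments. The documents support neither. ECG is also a weak example, because for completers sequence and treatment coincide at Day 29.

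What the reply does not remove is the conflict itself. SAP 2.1 is a general rule; SAP 5.0 is specific to safety and says treatment for laboratory values and vital signs. Table 47 and the adverse-event tables show that treatment is the SAP's own convention. Table 46's Day 29 contrast is there, but unlabelled and opposite in sign between rows.

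**Conclusion.** The point holds as an unrecorded departure from protocol 15.4 and 15.5 and, for laboratory values and vital signs, as a contradiction between SAP 5.0 and its shells. It affects Tables 46, 48, 49 and 50 and the ECG sentence. The consequence is that continuous laboratory and vital-sign values are nowhere summarized pooled by treatment, and that Table 46's Day 29 change is easily misread.

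The size is modest. On the assumed 12/11 split without dropout, each treatment's 23 observations appear as cells of 12 and 11. If 23 per sequence were enrolled, as the sample-size statement reads, the cells would be 23 and the pooled count 46, with the same layout problem. The precision ratios are illustrative, since they rest on assumed correlations and on a reader who compares sequences at one visit. For ECG the effect is on labels and on early withdrawals only. The contrasts remain recoverable, because Data Listings 4 and 5 carry treatment at collection or measurement. It is still worth correcting before lock, since it restores a summary that the protocol promises for a primary objective.

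**What to change.** - **Tables 46 and 48.** Group by treatment at the time of assessment: blinded amifampridine, blinded placebo and open-label amifampridine. Pool Day 8 and Day 29 observed values by treatment. Take change from one stated baseline common to both periods, and make SAP 5.0 and the footnotes agree on it. Screening and Day 0 both have laboratory and vital-sign data. Do not pool change from the previous assessment.
- **Optional addition.** A descriptive within-patient amifampridine-minus-placebo difference for laboratory values and vital signs. The protocol does not require it.
- **ECG.** Change the SAP sentence and Tables 49 and 50 to treatment at the time of the ECG. This relabels completers' Day 29 values and assigns early-withdrawal ECGs correctly. There is nothing to pool with Day 8, because no Day 8 ECG is scheduled. The Day 0 row in Table 49 should be reconciled with the schedule.
- **Listings.** Keep sequence there. Data Listing 15 has no column for treatment at the time of the ECG and needs one.
- **If sequence is intended.** Record the departure and its reason in the SAP, as protocol 15.6 requires.

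No new data are needed. The cost is shell and programming edits and, if by-visit rows are kept, slightly longer tables.
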